#### Local and General Unsolicited AEs

Any unsolicited AE which is recorded with the preferred term including the text “injection site” or “vaccination site” will be considered as a local reaction. Any other preferred terms which are considered as local events will be documented in the DRM minutes. Any unsolicited AE not classified as a local AE will be classified as a General AE.

### **3.4 Analysis Variables**

#### **3.4.1 Demographic and Other Baseline Characteristics**

##### Demographics

- Age
- Sex
- Race (American Indian or Alaskan Native, Oriental/Asian, Black/African American, Native Hawaiian/Other Pacific Islander, White/Caucasian, Other)
- Ethnicity (Hispanic or Latino, or Non-Hispanic or Latino)
- Height [cm]
- Body weight [kg]
- Body Mass Index (BMI)

##### Other Baseline characteristics

- History of smallpox vaccination or vaccination with other pox-virus based vaccine
- Medical history (including cardiac risk assessment, but excluding HIV/AIDS specific conditions)

- Non-treatment emergent AEs

#### HIV specific characteristics

- History of HIV infection
  - Circumstances [categories] of HIV infection
  - Year of diagnosis [Year] of HIV infection
  - Lowest CD4 count [cells/mL] previously documented
  - Lowest CD4 count [cells/mL] previously measured (nadir)
  - CD4 count [cells/mL] at Screening
  - Highest Viral Load [copies/mL] during up to six months ago
  - Viral Load [copies/mL] at Screening
- HIV related illnesses
- AIDS defining conditions

### **3.4.2 Safety Variables**

Physical examination (complete examinations at Visit SCR and targeted physical examination at all other visits).

Only abnormal physical examination results will be listed.

#### Vital signs (at each visit)

- Heart rate [beats per minute]
- Systolic and diastolic blood pressure [mmHg]
- Body temperature [°C]

#### 12-lead Electrocardiogram (ECG) (at SCR and Visit 2)

(Additional ECGs will be performed and reported if clinically indicated [e.g. Visit 4 or Visit 7], or in case of any clinically significant cardiac events are present)

- Investigator's overall interpretation (normal, abnormal)
- Clinical significance

#### Safety laboratory data (at Visit SCR, Visit 2, Visit 4 and Visit 7)

(Additional safety laboratory data will be obtained and reported if clinically indicated [e.g. FU 1 or 2]).

Clinical chemistry (serum)

- Total bilirubin
- Alkaline phosphatase (AP)
- Aspartate Aminotransferase (SGOT/AST)
- Alanine Aminotransferase (SGPT/ALT)
- Serum creatinine
- Low Density Lipoprotein (LDL) (only at Visit SCR)
- High Density Lipoprotein (HDL) (only at Visit SCR)
- Total cholesterol (only at Visit SCR)
- Sodium
- Potassium
- Calcium
- Troponin I

#### Hematology (whole blood)

- Red blood cell count
- Hemoglobin
- Total and differential WBC (Eosinophils, Basophils, Neutrophils - % and absolute, Lymphocytes, Monocytes)
- Platelet count
- Hematocrit, mean corpuscular/cell volume (MCV), mean corpuscular hemoglobin (MCH), mean corpuscular hemoglobin concentration (MCHC) and red blood cell distribution width (RDW)

#### HIV Related

- Viral Load (only at Visit SCR and Visit 2)
- CD4 count (at Visit SCR, Visit 2, Visit 4, Visit 7, Visit 8 and FU 1 and FU 2)

Pregnancy test (serum  $\beta$ -HCG pregnancy test at SCR and urine  $\beta$ -HCG pregnancy test within 24 hours prior to each vaccination and at last active trial phase visit for women of childbearing potential).

Information on all pregnancy tests will be listed.

#### Solicited local AEs reported in the subject memory aid (on days of vaccination and during the following seven days)

- Injection Site Erythema (Redness)

- Injection Site Swelling
- Injection Site Pain
- Injection Site Induration
- Injection Site Pruritus (Itching)

Solicited general AEs reported in the subject memory aid (on days of vaccination and during the following seven days)

- Body Temperature (Fever)
- Headache
- Myalgia (Muscle pain)
- Chills
- Nausea
- Fatigue

Unsolicited AEs reported (on days of vaccination and during the following 28 days)

- Other, unsolicited local and general adverse events following vaccination

SAEs

AESIs

In case an AESI is also an SAE it will be treated and reported as an SAE.

Prior and Concomitant medication

### **3.4.3 Immunogenicity Variables**

Seropositivity (yes/no) at Visits 1, 3, 4, 6, 7 and FU 1 and FU 2

- Vaccinia-specific neutralizing antibodies (PRNT)
- Total vaccinia-specific antibodies (ELISA)

Seroconversion (yes/no) at Visits 3, 4, 6, 7 and FU 1 and FU 2

- Vaccinia-specific neutralizing antibodies (PRNT)
- Total vaccinia-specific antibodies (ELISA)

Antibody titers at Visits 1, 3, 4, 6, 7 and FU 1 and FU 2

- Vaccinia-specific neutralizing antibodies (PRNT)
- Total vaccinia-specific antibodies (ELISA)

### **3.4.4 Pharmacokinetic Variables**

Not applicable

### **3.4.5 Pharmacodynamic Variables**

Not applicable

## **3.5 Analysis and Presentation Methods**

### **3.5.1 Listings and Descriptive Statistics**

All individual data entered in the eCRF and derived data will be listed as measured in the Individual Subject Data Listing.

For ELISA and PRNT titers descriptive statistics will be based on Geometric Means and confidence intervals (CI). Other, continuous measurements will be summarized by means of descriptive statistics (i.e. number of observations (N), mean, SD, minimum (Min), median, maximum (Max)) and categorical data will be summarized by means of frequency tables (i.e. count and percentages) and CI, if not stated otherwise.

All tables and listings will be sorted by scheduled visit (and subject, if appropriate).

All tables will be presented split by treatment groups (Groups 1 - 3).

Repeat assessments/measurements and unscheduled assessments/measurements will be included in the Individual Subject Data Listing. In case of any repeats of safety laboratory values, the repeat values will be used for the before-treatment assessment and the original value for the post-trial assessment. All other repeat values will be listed in a separate listing.

### **3.5.2 Software**

All statistical summaries and analyses of safety and efficacy data will be performed using SAS® 9.2 or higher (Statistical Analysis System, SAS-Institute, Cary, NC, USA) for Windows XP.

### **3.5.3 Primary Endpoint**

Occurrence, relationship and intensity of any serious and / or unexpected Adverse Events at any time during the trial.

All SAEs with onset from first injection of trial vaccine to FU 2 will be listed. An additional listing will also be prepared for the AESIs.

### 3.5.4 Disposition of Subjects

All subjects screened will be accounted for. For the active trial phase a summary table will be presented specifying:

- The number of subjects screened
- The number of subjects randomized to each group
- The number of subjects completing the active trial phase of the trial
- The number of subjects included in each analysis set
- The number of subjects withdrawn from the second vaccination
- The number of subjects within Group 3 withdrawn from the third vaccination
- The number of subjects prematurely discontinuing the trial (as well as the frequency of primary reasons for withdrawal/premature discontinuation)
- The number of subjects completing the respective FU 1 and FU 2 Visits.

A listing will present all randomized subjects, time and date of completion or discontinuation with date of last dose of trial medication, date of discontinuation, reason for discontinuation and primary reason for withdrawal from any vaccination, if applicable.

All screening failures (subjects not eligible for the trial) will be listed including the reason why not eligible. Listings will also be presented for all violations in inclusion criteria and all exclusion criteria fulfilled.

### 3.5.5 Demographic and Other Baseline Data

All listings will be based on the screened subjects with screen failures and subjects randomized but not treated considered as two separate trial groups. However tables of the descriptive statistics for the demographics will only be produced for the FAS and PPS.

Descriptive statistics will be presented for the continuous demographic variables, age, height, and body weight. Note that the value obtained on the date of the actual Screening Visit is used for age, height and body weight calculations (hence also for BMI) and not the date of any partial Re-screening Visit.

Age is calculated using the following formula:

AGE = Year of Screening Visit – Year of Birth;  
if Month of Screening Visit < Month of Birth then AGE → AGE – 1;  
if Month of Screening Visit = Month of Birth  
and Day of Screening Visit < Day of Birth then AGE → AGE – 1

Frequencies and percentages of subjects will be tabulated for the categorical variables sex, race and ethnicity in the same table by treatment group and overall. Percentages will be based on the total number of subjects in the relevant population.

Descriptive statistics for the demographic data will be produced by treatment group.

A summary of medical history by Preferred Term (PT) and System Organ Class (SOC) will be produced for each treatment group.

Non-treatment emergent AEs will be listed by body system and preferred term. Relative day of onset and duration of non-treatment emergent AEs will be calculated as described in [Section 3.3.3](#). Pre-treatment Adverse Events are defined as AEs with start date after the subject was screened for the trial but before the first injection was received. These events are to be reported.

Frequency summaries of the history of HIV infection, AIDS defining conditions, circumstances of HIV infection, and HIV related illness will be produced by treatment group.

Summary statistics of the historical viral load and CD4 statistics (year of diagnosis, lowest CD4 count previously documented, CD4 nadir, CD4 count at screening, highest viral load during up to six months ago, viral load at screening) will also be presented stratified by treatment group.

### **3.5.6 Prior and Concomitant Medication**

All prior medication will be summarized by Anatomical-Therapeutical-Chemical (ATC) class and Generic name according to the 2014/Q3 version of the World Health Organization Drug Dictionary (WHO-DD). All concomitant medication will be summarized by ATC class and Generic name for all subjects in the FAS.

The table/listing “Prior medication” includes the medication data where end date is before date of first injection of trial vaccine. The table/listing “Concomitant medication” includes ongoing medication or medication with missing end date or with end date after date of first injection of trial vaccine.

All listings will display the original dates as captured in the eCRF.

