### **8.2.2 Prior and Concomitant Medications**

All concomitant (ongoing) medication except homeopathic substances and dietary supplements must be recorded in the eCRF and the subject's medical record including information about the indication, dosage regimen, and the onset and end of treatment.

The following medication, taken within three months prior to screening, will also be recorded in the eCRF and the subjects medical record: vaccines, corticosteroids (via any route of administration), other immune-modulating drugs, immunoglobulin and/or any blood products, investigational drugs and depot preparations which are still active at the date of SCR.

The antiretroviral medications, taken within six months prior to SCR, will also be recorded in the eCRF and the subject's medical record.

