### Trial Day

The individual subject's day of trial is calculated from the day of the first injection. The day of first injection is defined as Day 0 and the day after first injection is Day 1, and so on. Equally, the day before first injection is defined as Day -1, and so on. In particular, no reference is made to the time of the injection in the calculation of the trial day, i.e. at midnight a new trial day begins regardless of the time of first injection. Note that it is possible for Visit 1 to be performed, for example, on trial Day -1.

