### 3.3 Definitions, Data Conventions and Handling of Missing Data

#### 3.3.1 Missing Data

No imputation of missing titers will be performed.

For the analysis of safety data incomplete AE and medication start and end dates will be imputed in order to assign these events to the correct vaccination period.

Missing Vital Signs data for Visit 1 will be imputed using screening (or latest re-screening) values. However, this will be displayed as 'Baseline' values in the tables and listing for Vital Signs data without reference to whether the data originated from Visit 1 or SCR.

For prior and concomitant medication and AEs imputation of partial start and end dates will be done for analysis purpose according to the following rules:

Missing	Rule for start date	Rule for end date	Flag for imputation
Day	First of month*	Last of month*	D
Month †	1. January*	31. December*	M
Year †	no imputation	Last visit date	Y

\* Unless the imputed start date is before first visit date, in which case first visit date is used; or the imputed end date is after last visit date in which case last visit date available is used.

† It is assumed that a missing month implies a missing day as well, and that a missing year implies a missing month and day.

All data will be listed and summarized as captured in the eCRF. All listings will display the original dates as captured in the eCRF.

If the imputation of a partial start date of an AE leads to a start date prior to the date of first vaccination, it will be set to the date of first vaccination following the worst case principle.

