##### 15.1.4 Prior and Concomitant Medication

- 15.1.4.1 Prior Medication, by ATC Class and Generic Name – FAS
- 15.1.4.2 Concomitant Medication, by ATC Class and Generic Name – FAS
- 15.1.4.3 Concomitant HIV-Related Medication – FAS

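### SAP 3.5.6 assigns a medication that ends on the date of first injection to neither the Prior nor the Concomitant output

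*SAP*

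**What the plan says.** SAP 3.5.6 (Prior and Concomitant Medication) gives one definition per category and applies it to both the table and the listing. The Prior output "includes the medication data where end date is before date of first injection of trial vaccine". The Concomitant output takes a drug that is ongoing, or "medication with missing end date or with end date after date of first injection of trial vaccine".

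The rules feed Tables 15.1.4.1 (Prior) and 15.1.4.2 ("Concomitant Medication, by ATC Class and Generic Name"), and Listings 16.2.1.4.1 and 16.2.1.4.2. The SAP index also has a table and a listing of concomitant HIV-related medication (15.1.4.3 and 16.2.1.4.3), with no separate definition of their own.

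On the collection side, Protocol 8.2.2 says that concomitant medication, homeopathic substances and dietary supplements apart, "must be recorded in the eCRF and the subject's medical record including information about the indication, dosage regimen, and the onset and end of treatment".

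**The concern.** A rule that sorts records into Prior and Concomitant should place each record in exactly one of the two. Here one calendar date, the date of first injection, falls between them.

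That date matters more than most. Protocol 4.2.2 keeps subjects under observation for at least 30 minutes after each vaccination with medical treatment at hand, and immediate adverse events are recorded. A single treatment given in that period starts and ends on Day 0. In a trial with a safety primary objective, a reader of the report would expect to find it in the concomitant medication table. Under the rule as written it would not be there, and nothing in the output would show that it was missing.

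**Working it through.** There is no figure in the plan to reproduce. The check is one of logic.

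**Inputs.** Let D0 be the date of first injection and E the end date of a medication.
- Prior (SAP 3.5.6): E < D0.
- Concomitant (SAP 3.5.6): ongoing, or E missing, or E > D0.
- Time scale (SAP, Trial Day): "The day of first injection is defined as Day 0 and the day after first injection is Day 1, and so on"; in addition, "no reference is made to the time of the injection in the calculation of the trial day".

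**The rules applied to end dates around the boundary.**

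| End date | Prior (E < D0) | Concomitant, as written (E > D0, ongoing or missing) | Concomitant, if E ≥ D0 were used |
|---|---|---|---|
| Day -28 | yes | no | no |
| Day -1 | yes | no | no |
| Day 0 | no | **no** | yes |
| Day 1 | no | yes | yes |
| Day 28 | no | yes | yes |
| Missing | no | yes | yes |

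As written, Day 0 is the only row that falls in neither category. With equality included in the Concomitant rule, every row falls in exactly one.

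**Does another rule in the SAP close the gap?**
- *Clock time.* Both medication definitions are by date, and the trial-day convention ignores the time of injection. Time of day cannot break the tie.
- *Imputation.* SAP 3.3.1 says: "For prior and concomitant medication and AEs imputation of partial start and end dates will be done for analysis purpose". It acts on partial dates, so a complete Day 0 end date stays as it is. It can also produce one. An end date with only the day missing is set to the last day of its month, and this equals D0 when the first injection fell on that day. SAP 3.5.6 does not say whether a partial end date counts as missing. If it does, such a record goes to Concomitant and this second route closes.
- *Same-day convention.* SAP 3.3.2 says what to do when an adverse event has no start time and begins on a vaccination date: it goes to that vaccination's period. There is no counterpart for medication.
- *Discretion.* The SAP's opening section says the plan will be followed completely, and SAP 3.6 lists no alterations. A programmer has no written basis for choosing ≥ over >.

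**How far the gap reaches.** It exists at the first injection only. A drug that ends on the date of the second or booster vaccination ends after D0 and is Concomitant. A drug given on Day 0 that continues to Day 1 or later, is ongoing, or has no end date is also Concomitant.

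**The case against.** Several points on the other side are sound.

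- *The data are not lost.* Protocol 8.2.2 requires collection, and SAP 3.3.1 and 3.5.1 both commit in general terms to listing all eCRF data. A reader might infer that a Day 0 record disappears from the report altogether. The documents do not support that. What stands is narrower: the only indexed medication listings are Prior, Concomitant and Concomitant HIV-Related, so no listing would clearly hold the record. A general promise and a specific rule are in conflict.
- *Ongoing can be read broadly.* Protocol 8.2.2 treats concomitant and ongoing as near synonyms. On that reading, a course in progress up to Day 0, including an antiretroviral stopped that day, could count as Concomitant. A drug both started and stopped on Day 0 after the injection remains unassigned.
- *Premedication.* A reader might think of routine analgesic or antipyretic premedication. Neither document mentions any, so it is not used as evidence here.
- *Per Protocol Set.* Unallowed medication is an example of a major deviation in SAP 3.2.2, so a reader might infer that the data review meeting would miss a prohibited drug given on Day 0. Nothing says the meeting works from these listings, decisions are made case by case, and protocol deviations have their own listing (16.2.1.1.7).
- *Reactogenicity and seriousness.* A reader might infer that solicited-event results or the primary endpoint are distorted. No planned analysis adjusts, stratifies or censors by medication use. Immediate events are recorded directly, events are graded without reference to the medication tables, and Protocol 9.4.2 has each SAE described individually.

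**Conclusion.** The boundary error is certain on the text of SAP 3.5.6, and its effect is small. A medication with an end date equal to the date of first injection belongs to neither category, so the Prior and Concomitant tables and their listings are incomplete as specified. The clear case is a drug started and stopped on Day 0.

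The effect stops at descriptive medication outputs at the first injection. The primary endpoint, adverse event incidences, GMT ratios, seroconversion differences, sample size and error rates are unchanged.

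The documents give no frequency of medication ending on Day 0, so the number of records or subjects cannot be derived and none is claimed. The conclusion assumes that the SAP wording is programmed literally and that a one-time Day 0 treatment is entered with its end date, as Protocol 8.2.2 indicates.

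**What to change.** In SAP 3.5.6, define Concomitant as ongoing, missing end date, or end date on or after the date of first injection. Leave the Prior definition as it is. The two sets then cover every record without overlap. State that the same rule governs Table 15.1.4.3 and Listing 16.2.1.4.3 (concomitant HIV-related medication).

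The cost is a few words in the SAP and one comparison operator in the program, before database lock. Concomitant counts may rise slightly. They will include a few drugs taken on Day 0 before the injection, because calendar dates cannot separate these from drugs given after it. That is an acceptable price for a complete classification.

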### **3.5.7 Compliance**

Compliance will be evaluated with respect to the number vaccinations received and the number of memory aids completed.

### **3.5.8 Immunogenicity Analysis**

All immunogenicity results will be listed. Tables and figures will be prepared for the PPS and the FAS. All of the following analyses will be performed for results generated using both the PRNT and ELISA.

### Seropositivity rates

Vaccinia-specific seropositivity rates will be presented by treatment group for Visits 1, 3, 4, 6, 7, FU 1 and FU 2 along with the Clopper-Pearson 95% confidence intervals (CIs) of the seropositivity rates.

### Seroconversion rates

Vaccinia-specific seroconversion rates measured by ELISA and PRNT will be presented by treatment group for Visits 3, 4, 6, 7, FU 1 and FU 2 (and for combined groups as indicated) along with the Clopper-Pearson 95% CIs of the seroconversion rates.

In addition, the difference in seroconversion rates of Group 2 at Visit 4 will be compared to the combined Group 1 / Group 3 seroconversion rates and will be calculated as

Difference in seroconversion rates =

$$\{ \text{Group 2 seroconversion rate} \} - \{ \text{combined Group 1 and Group 3 seroconversion rate} \}$$

along with an exact 95% CI calculated following the “Invert two one-sided tests” method of Chan and Zhang ([Chan, 1999](#)).

Similarly, the difference between the seroconversion rate at Visit 7 for Group 3 and the seroconversion rates at Visit 4 for Group 1 and Group 2 (separately) will also be calculated along with the exact 95% confidence interval.

For both the FU Visits (FU 1 and FU 2) the difference of the seroconversion rate for Group 3 will be compared to the seroconversion rate of Group 1 and Group 2 separately.

Lastly, the difference of the seroconversion rates for Group 1 will be compared to the seroconversion rates of Group 2 and Group 3 separately at Visit 3, Visit 4, FU 1 and FU 2.

A bar chart will be presented showing the seroconversion rates measured by ELISA and PRNT per treatment group for each visit for the PPS and the FAS.

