## 4 Trial Design

### 4.1 Experimental Design

Randomized, open-label Phase II trial to assess the safety and immunogenicity of MVA-BN® smallpox vaccine when increasing the number of injections compared to the standard regimen in immunocompromised subjects with HIV infection

In total, 90 vaccinia-naïve subjects will be enrolled in this trial (see [Table 4](#)). All subjects will be randomly assigned (1:1:1) to Group 1, Group 2 or Group 3. Group 1 will receive the standard regime – two vaccinations at Day 0 and Day 28. Group 2 will receive two injections at each vaccination day in the standard schedule and Group 3 will receive the standard regime and an additional early boost 12 weeks after the first dose of the standard vaccination schedule with MVA-BN® smallpox vaccine.

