#### **5.1 Recruitment Procedure**

Subjects will be recruited actively. Recruitment strategies, including IRB approved advertisements, will be evaluated by the Sponsor.

30 subjects will be enrolled in each group (90 in total).

---

After signing the ICF and HIPAA, subjects undergo screening procedures to check eligibility according to the inclusion/exclusion criteria. In the event of a screening failure secondary due to mild or limited acute illness or abnormal laboratory values, the subject may be re-screened after resolution of the event. Re-screening may require only an additional blood draw or a complete re-screening evaluation, depending on the circumstances of and the time interval from the initial screening failure (see also [Section 4.2.1](#)).

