## 7.1 Humoral Immunogenicity

Immunogenicity testing will be performed on samples obtained from subjects of all three groups on trial Visit 1, Visit 3, Visit 4, FU1 and FU 2. Further, immunogenicity testing will be performed on samples obtained from subjects of Group 3 on trial Visits 6 and 7. Blood samples obtained on vaccination visits (i.e., Visit 1, Visit 3 and Visit 6) will be drawn prior to vaccination.

Antibody responses to MVA-BN® smallpox vaccine will be measured using a vaccinia-specific ELISA and vaccinia-specific PRNT, both assays established and validated at BN. The immunogenicity analysis will be performed at BN. All personnel involved in immunogenicity testing will be blinded to subject randomization details.

The procedures for the analytical tests performed are outlined in [Sections 7.1.1](#) and [7.1.2](#) below. The SOPs, effective at the time of testing will be filed in the electronic Trial Master File.

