## **1 Trial Overview**

### **1.1 Trial Description**

This trial is a randomized, open-label Phase II trial to assess the safety and immunogenicity of MVA-BN smallpox vaccine when increasing the number of injections compared to the standard regimen in immunocompromised subjects with HIV infection.

In total, ninety (90) vaccinia-naïve Human Immunodeficiency Virus (HIV) infected subjects will be enrolled in this trial. All subjects will be randomly assigned (1:1:1) to one of three groups (Groups 1-3) to receive:

Group 1:

One injection at Day 0 and Day 28 with 0.5 mL Modified Vaccinia Ankara Strain – Bavarian Nordic (MVA-BN) smallpox vaccine containing at least  $1 \times 10^8$  Tissue Culture Infectious Dose 50% (TCID50) per mL (standard regimen)

Group 2:

Two injections at Day 0 and two injections at Day 28 with 0.5 mL MVA-BN smallpox vaccine each containing at least  $1 \times 10^8$  TCID50 per mL (double dose regimen)

Group 3:

One injection at Day 0 and Day 28 with 0.5 mL MVA-BN smallpox vaccine containing at least  $1 \times 10^8$  TCID50 per mL (standard regimen) and one booster injection at Day 84 (Week 12) with 0.5 mL MVA-BN smallpox vaccine containing at least  $1 \times 10^8$  TCID50 per mL (booster regimen)

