### Geometric Mean Titers (GMTs)

GMTs measured by ELISA and PRNT will be calculated at Visits 1, 3, 4, 6, 7, FU 1 and FU 2 for each treatment group and for combined groups as indicated.

Descriptive statistics will be derived by visit including number of observations available at each visit (n) and GMT with 95% CI (derived by the antilogarithm of the 95% CI of the  $\log_{10}$  titer transformations). GMTs and upper and lower confidence limits will be displayed to one decimal place.

The ratio of the GMTs will be presented between Group 2 and the combined Group 1 / Group 3 at Visit 4 along with the 95% CI. Similarly, the ratio of the GMTs will be presented between

Group 3 at Visit 7 and Group 1 / Group 2 separately at Visit 4, and at the FU Visits (FU 1 and FU 2) the ratios of the GMTs will be presented between Group 3 and Group 1 / Group 2 separately. Lastly, the ratios of the GMTs at Visit 1, 3, 4, FU 1 and FU 2 will be presented between Group 1 and Group 2 / Group 3 separately.

A line chart will be presented showing the GMTs measured by ELISA and PRNT per treatment group for each visit for the PPS and the FAS.

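### At Visit 3 the double-dose contrast uses Group 1 alone as comparator, although Group 3 has had the same single injection; adding a pooled contrast would recover the 25% of available information left unused

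*SAP*

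**What the plan says.** Protocol 4.1 sets out the regimens: "Group 1 will receive the standard regime", and "Group 3 will receive the standard regime and an additional early boost 12 weeks after the first dose". Allocation is 1:1:1 with 30 subjects per group. Protocol 7.1 takes serum from "subjects of all three groups on trial Visit 1, Visit 3, Visit 4, FU1 and FU 2", and at vaccination visits the blood is drawn before the injection.

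SAP 3.5.8 plans these contrasts while Groups 1 and 3 are still on the same regimen:

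- **Visit 4, pooled:** GMT ratios between "Group 2 and the combined Group 1 / Group 3 at Visit 4", and the matching difference in seroconversion rates.
- **Seroconversion, separate:** Group 1 is "compared to the seroconversion rates of Group 2 and Group 3 separately at Visit 3" and at Visit 4 (and at FU 1 and FU 2, after the booster).
- **GMT ratios, separate:** at Visits 1, 3 and 4 (and at FU 1 and FU 2) these "will be presented between Group 1 and Group 2 / Group 3 separately".

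The separate contrasts carry out a listed secondary endpoint (protocol synopsis; SAP 1.4.2), which compares Groups 2 and 3 separately with Group 1 at the remaining sampling points. SAP 3.5.8 also allows summaries for combined groups where indicated, but the only combination indicated is at Visit 4.

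**The concern.** Visit 3 is the only sample that isolates the response to the first vaccination: one injection in Groups 1 and 3, two in Group 2. It is also the only post-baseline visit where the pooling logic applies but is not used. Visits 2 and 5 have no immunogenicity draw, Visit 6 is for Group 3 only, and after the booster the regimens differ.

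The reasoning that justifies pooling at Visit 4 holds equally at Visit 3, and the SAP gives no reason for treating the two visits differently. Half of the subjects on the standard regimen (30 of 60) stay out of the Group 2 contrast.

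At stake is how precisely the trial can say whether a double first dose raises the early response. Protocol 2.6.4 reports ELISA seroconversion in healthy volunteers of 81 to 100% after the first standard dose and 100% after the second. If HIV-infected subjects behaved similarly, which is an assumption, Visit 3 would leave more room than Visit 4 to see an ELISA seroconversion difference.

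A smaller point is that Group 3 versus Group 1 before the booster compares identical treatment, and the SAP does not label it as a balance check.

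**Working it through.** **Inputs.** 30 per group (protocol 4.1 and 5.1). SD of log10 titer 0.85 for PRNT and at most 0.42 for ELISA; two-sided 5% two-group t-test; 80% power at 0.74 SD (SAP 3.1).

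**Step 1: reproduce the plan's figure.** For 30 versus 30 and a difference of 0.74 SD, the noncentral t distribution gives power of 80.5%, and the difference detectable with 80% power is 0.736 SD. On the titer scale, 0.74 × 0.85 = 0.629 (10^0.629 = 4.26-fold) and 0.74 × 0.42 = 0.311 (10^0.311 = 2.05-fold). The SAP's 80%, factor of 4 and factor of 2 are confirmed.

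**Step 2: standard error of the Visit 3 contrast, in SD units.**

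- Planned, 30 versus 30: √(1/30 + 1/30) = 0.2582.
- Pooled, 30 versus 60: √(1/30 + 1/60) = 0.2236.
- Ratio: 0.2236 / 0.2582 = 0.866, so the SE falls by 13.4%.
- Variance ratio: (1/20) / (1/15) = 0.75, so the planned contrast gives up 25% of the information.

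The ratio does not depend on the SD, nor on the number evaluable if the groups stay equal: (1/n + 1/2n) / (2/n) = 0.75 for any n.

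**Step 3: 95% CI factor for a GMT ratio.** Factor = 10^(t × SD × SE). Planned: t(58 df) = 2.0017, and 2.0017 × 0.2582 = 0.5168. Pooled: t(88 df) = 1.9873, and 1.9873 × 0.2236 = 0.4444.

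| SD of log10 titer | Planned, 10^(0.5168 × SD) | Pooled, 10^(0.4444 × SD) |
|---|---|---|
| 0.42 (ELISA, SAP 3.1) | 1.65 | 1.54 |
| 0.60 (assumed) | 2.04 | 1.85 |
| 0.85 (PRNT, SAP 3.1) | 2.75 | 2.39 |
| 1.00 (assumed) | 3.29 | 2.78 |

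The assumed rows are there because SAP 3.1 does not tie its SDs to a visit. Titers below the detection limit are set to 1, which could change the spread after one dose.

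**Step 4: the same gain on the SAP's power scale.** With 30 versus 60, power at 0.74 SD is 90.5%. The detectable difference at 80% power is 0.633 SD. For PRNT that is 0.633 × 0.85 = 0.538 log10 (about 3.5-fold); for ELISA it is 0.633 × 0.42 = 0.266 log10 (about 1.85-fold).

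**Step 5: seroconversion, illustration only.** The documents give no expected rates for this population. With assumed rates and a normal approximation (the SAP's interval is exact, so these are indicative), power moves from planned to pooled as follows:

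- 50% versus 80%: 69% to 81%.
- 60% versus 85%: 59% to 69%.
- 60% versus 90%: 78% to 88%.
- 70% versus 95%: 73% to 83%.

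**Step 6: fewer evaluable subjects in Group 3.** If only m Group 3 subjects are evaluable and Groups 1 and 2 keep 30 each, the variance ratio is (1/30 + 1/(30 + m)) / (2/30). For m = 25 it is 0.773 (SE 12.1% lower). For m = 20 it is 0.800 (SE 10.6% lower). These values of m are assumptions.

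**The case against.** The strongest reply is that nothing here is an error. The separate Visit 3 contrast is a pre-specified secondary endpoint in the protocol, and the SAP carries it out as written. The primary endpoint is safety and is analysed descriptively. No test or success criterion hangs on Visit 3. The sample size was set for 30 versus 30, so the planned contrast has its designed precision. Protocol 2.6.4 places peak titers two weeks after the second vaccination, which explains why Visit 4 is the featured comparison. All of this stands, and it limits the point to a gain in precision.

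A second objection also stands. The main immunogenicity analysis is on the PPS, where Group 3 subjects must complete Visits 6 to 8 and have Visit 7 titers (SAP 3.2.2). Group 1 has no such requirement, so the two groups are selected differently and pooling them there is not free. The planned Visit 4 pooling has the same feature, and the FAS does not require the later visits.

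Three stronger readings are tempting, and the documents do not support them:

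- **That a third of the data is discarded.** One third is the share of subjects outside this one contrast; the information loss is 25%. Group 3's Visit 3 rates and GMTs are still tabulated with intervals and compared with Group 1.
- **That the SAP departs from the protocol.** It follows the protocol's endpoint wording, so the gap begins there.
- **That the pooled contrast should replace the separate one.** This would drop a required endpoint. The Group 3 versus Group 1 comparison is also useful, since it helps show whether pooling is reasonable.

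**Conclusion.** The point holds as a modest, cheap improvement. At Visit 3 the SAP compares Group 2 with half of the available standard-regimen subjects, while two weeks after the second vaccination it compares Group 2 with all of them. The cost is precision on a secondary contrast; the planned estimate is unbiased and no figure in either document is wrong.

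The 25% and 13.4% rest only on equal numbers evaluable and a common SD. The CI factors also assume 30 evaluable per group and that the SAP 3.1 SDs hold at Visit 3. The gain is somewhat smaller if Group 3 loses subjects from the PPS.

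**What to change.** In SAP 3.5.8, add Group 2 versus combined Groups 1 and 3 at Visit 3, for the seroconversion difference and the GMT ratio, each with a 95% CI, for both assays, in the PPS and the FAS.

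Keep the separate Group 2 versus Group 1 and Group 3 versus Group 1 contrasts. Label Group 3 versus Group 1 before the booster as a balance check: GMT ratios at Visits 1, 3 and 4, and seroconversion at Visits 3 and 4.

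Record the addition in SAP 3.6, which now lists no alterations from the protocol. State that the PPS result is to be read alongside the FAS result, because Group 3's PPS membership depends on Visits 6 to 8 and Visit 7 titers. The same note belongs with the planned Visit 4 pooling.

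The cost is one more row per assay in the existing comparison tables; no new data, visits or procedures are needed. It should be done before database lock, since the SAP's introduction requires analyses added later to be flagged as unplanned.
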